### *Data Analysis*

We calculated the net  $\dot{VO_2}$  by subtracting the seated rest  $\dot{VO_2}$  from the gross  $\dot{VO_2}$  over a 2-minute period of steady-state locomotion. Visual3D filtered marker trajectories and GRF data using 4th-order low-pass Butterworth filters with cut-off frequencies of 6-Hz and 10 Hz, respectively. We then built an 8-segment model consisting of the trunk, pelvis, thighs, shanks, and feet in Visual3D (C-Motion, Germantown, MA) with segment inertial properties from (Dempster, 1955; Hanvan, 1964). The inertial properties for the prosthesis were adjusted according to (Ferris et al., 2017).

### *Statistical Analysis*

As there was variability in the type of activity performed during metabolic testing, we only report individual data and relate changes to reported minimal detectable change (MDC) values where appropriate (Davidson et al., 2016). For kinematic and kinetic measures, we first took the average across five strides for walking and 30-s for running. Due to the small sample size, we calculated effect size, as Hedge's  $g$  for these measures. These are interpreted as small for  $|g| \geq 0.2$ , medium for  $|g| \geq 0.5$ , and large for  $|g| \geq 0.8$  (Cohen 1988).

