### *Experimental Protocol*

This study was a repeated measures design of three prostheses: the Caesar foot, AllPro, and participants' prescribed walking and running feet. Each foot was tested on a separate day, with the order of testing randomized. In the CAESAR and AllPro sessions, a certified prosthetist fit and aligned the prosthetic foot. The participant then walked, jogged, and walked on stairs. The prosthetist made adjustments until both the participant and prosthetist were satisfied with the fit/alignment. This process took approximately 20 - 45 minutes.

For each session, participants arrived at the lab having fasted and avoided caffeine for a minimum of 4 hr. Participants first completed metabolic testing on a treadmill. Participants remained seated for 5 minutes, while a K5 portable metabolic system (Cosmed, Rome, Italy) measured their resting metabolic rate of oxygen consumption ( $VO_2$ , mL/kg/min). Participants then ran continuously for 5 min at a self-selected speed on a treadmill. If they were uncomfortable or unable to run for 5 minutes without significant hand support, they instead walked for 8 minutes at a fixed speed based on their leg length that approximately self-selected speed in this population (Gates et al., 2013).

Participants subsequently completed a series of ambulatory tasks including walking at a fixed speed based on leg length, walking at self-selected slow, comfortable, and fast speeds, walking up and down a 3-step instrumented staircase (Bertec, Columbus, OH), and walking up

and down a 7.5° ramp at self-selected speed. After each task, participants were asked to provide feedback on their comfort and stability on a 100-mm visual analog scale. During the CAESAR session, participants completed stair and ramp walking twice, once with the foot in ‘run’ mode and then with the foot in ‘walk’ mode. We then asked which mode they preferred for that task and why.

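### Should net oxygen uptake also be summarised as a paired mean with a confidence interval, rather than as individual data only?

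*Combined protocol and SAP*

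**What the plan says.** The Experimental Protocol section sets up within-person comparisons: "This study was a repeated measures design of three prostheses", each tested on its own day in random order. The third condition is the participant's own "prescribed walking and running feet". For metabolic testing the default task is a run: "Participants then ran continuously for 5 min at a self-selected speed on a treadmill". Participants who were uncomfortable running, or could not run for that time without significant hand support, had a substitute task: "they instead walked for 8 minutes at a fixed speed based on their leg length".

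The Data Analysis section defines the outcome as steady-state oxygen uptake minus seated resting uptake. The Statistical Analysis section then gives the reporting rule, "As there was variability in the type of activity performed during metabolic testing, we only report individual data", and adds that the authors "relate changes to reported minimal detectable change (MDC) values where appropriate". Kinematic and kinetic measures are treated differently: "Due to the small sample size, we calculated effect size", in the form of Hedges' g.

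**The concern.** The only reason given for withholding a group summary of oxygen uptake is that activity varied. That reason rules out pooling runs with walks, and it rules out a pair in which one person ran on one foot and walked on the other. It does not, by itself, rule out averaging within-person changes where activity and speed were the same on both feet. Walk-walk pairs should be matched on speed, because walking speed is set by leg length. The CAESAR-AllPro contrast looks well suited to a mean, since stiffness similarity was checked between these two feet and "In the CAESAR and AllPro sessions, a certified prosthetist fit and aligned the prosthetic foot".

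The small sample is not the stated reason either: for the biomechanical measures it led to a group effect size, not to omitting one. What would be at stake is a modest change shared by several people. An MDC is a threshold for one person's change, so a consistent average below it would appear only as a row of sub-threshold values, with no mean and no interval.

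**Working it through.** The plan states no figure for this outcome, so there is nothing to reproduce. Three checks are possible.

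**1. Is the stated reason sound?** A simulation under assumed values (net uptake 30 running and 10 walking in mL/kg/min, true foot effect -5%, noise 5% of level per measurement, n = 8, half of them runners) gives:

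- activity matched in every pair: mean change -4.8%, 95% half-width about 5.4 percentage points;
- 25% of participants switch activity between feet: mean change about +11%, half-width about 52 points.

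Unmatched pairs therefore destroy the average, and the plan is right not to pool them. Matched pairs could be averaged. The documents do not say how many there are.

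**2. What would a matched mean add?** For n matched pairs the 95% half-width, in standard deviations (SDs) of the paired difference, is t(0.975, n-1)/√n:

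| n | Calculation | Half-width (SDs) |
|---|---|---|
| 3 | 4.303/1.732 | 2.48 |
| 4 | 3.182/2 | 1.59 |
| 5 | 2.776/2.236 | 1.24 |
| 6 | 2.571/2.449 | 1.05 |
| 7 | 2.447/2.646 | 0.92 |
| 8 | 2.365/2.828 | 0.84 |

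To put this on the MDC scale, assume MDC95 = 1.96 × √2 × SEM, where SEM is the standard error of measurement (the documents give neither the level nor the value). Let v be the variance of the paired differences divided by 2 × SEM². The half-width in MDC95 units is then t(0.975, n-1) × √v / (1.96 × √n):

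| n | v = 1 (measurement noise only) | v = 2 | v = 4 |
|---|---|---|---|
| 3 | 1.27 | 1.79 | 2.53 |
| 4 | 0.81 | 1.15 | 1.62 |
| 5 | 0.63 | 0.90 | 1.27 |
| 6 | 0.54 | 0.76 | 1.07 |
| 7 | 0.47 | 0.67 | 0.94 |

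The benefit claimed for the mean is that it reveals a consistent change smaller than one MDC. Taking the observed SD as equal to the assumed one, the interval excludes zero only if the mean exceeds the half-width. At n = 4 with v = 2 or 4, no average below one MDC can do so. With v = 1, only averages between 0.81 and 1 MDC can. The half-width first falls below one MDC at n = 4, 5 or 7 for v = 1, 2 or 4. These counts apply to each stratum, because walkers and runners must be kept apart. Nothing in the documents shows that any stratum reaches them.

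**3. Can the matched subset be defined cleanly?** The Experimental Protocol section leaves four points open:

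- The switch from running to walking depends on comfort and ability. Whether it was decided once or at each session is not stated. If at each session, the foot may influence it, and dropping unmatched pairs drops those in which the foot changed running ability.
- Running speed is self-selected and not stated to be constant across days. Requiring equal speeds would again select on something the foot may affect. It would also need a tolerance, and the protocol is written in the past tense, so a tolerance chosen now could be post hoc.
- Whether treadmill speed was recorded is not stated.
- The CAESAR foot has a run mode and a walk mode. The mode used for metabolic testing is not stated, so pairs matched on activity and speed could still mix modes.

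**The case for a change.** The strongest case for the added summary is that it costs little: a sentence or two and a small table, with the individual data kept as the main display, the mean labelled descriptive, and no mean shown for strata of two or three people. Even a wide interval tells the reader how little the group data exclude. The count of matched pairs would be informative in itself, because the documents do not say how many participants ran, walked or switched. Readers can average the individual values themselves only if activity and speed are shown for each session, and the plan does not promise that.

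Much of this stands. Varied activity does not logically forbid a matched mean, and with seven or eight matched pairs in one stratum the interval could be useful. It does not turn the omission into an error. If every stratum has three people or fewer, the addition reduces to a count. A descriptive label would not tell the reader that the subset is selected. The comparison with Hedges' g is weak as well: the level-walking, stair and ramp tasks have no substitute activity, whereas the metabolic test does. Running biomechanics are also summarised, so the contrast is not complete, but treating oxygen uptake more cautiously is not inconsistent. The qualifier on the MDC comparison, that it is made where appropriate, may already keep unmatched pairs out of it.

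**Conclusion.** The concern does not hold. The plan states its rule and its reason, the reason correctly bars the averages that would mislead, and individual changes read against an MDC are a legitimate analysis for a small repeated-measures study. No result produced under the rule would be wrong. What is missing is an optional supplementary summary whose value cannot be established from the documents: under the assumptions above, its half-width ranges from 0.81 to 1.62 MDC95 at four matched pairs and from 0.47 to 0.94 at seven, with the actual number unknown. Against that uncertain gain stands a real risk of selecting on running ability or speed. A statistician could reasonably choose either way. This judgement rests on the absence of any stated sample size or matched-pair count. A large stratum of speed-matched pairs would make the summary more attractive, but its omission would still not be a fault.
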